7.2.3. Analysis for Secondary Endpoints

7.2.3.1. PK and PD Analysis

Plasma concentration of napabucasin and amcasertib will be listed. Nominal times, actual PK sample collection times and dose will be included in the listing.

PD data will be listed if available.

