
# solely by RECIST 1.1 criteria or mRECIST criteria for patients with HCC, provided that the patient is obtaining potential clinical benefit in the opinion of the investigator. It is expected that most patients will receive between 4 and 24 weeks of treatment. **Pharmacokinetic** Pharmacokinetic variables to be determined include maximum plasma drug and concentration (Cmax), time to reach Cmax (Tmax), area under the time-**Pharmacodynamic** concentration curve (AUC), and terminal half-life. Variables: Blood samples for PK analyses will be performed on Cycle 1, Days 15-16 and on Cycle 2, Day 15 of the phase Ib portion. During the phase II portion, approximately six patients will collect PK as Phase I schedule, then a single pharmacokinetic blood draw may be obtained on Cycle 2, Day 15. Paraffin embedded tumor tissue is requested from all patients prior to initiation of protocol therapy. Patients may enroll if they do not have archival tissue. Patients may enroll if they are not aware if they have archival tissue. Pharmacodynamic studies as well as the concentration of study drug (either BBI608 or BBI503) in tumors will be examined following study drug administration in patients with accessible tumors who consent to an optional onstudy biopsy. This optional biopsy will be obtained on Cycle 2, Day 15. **Statistical Methods:** Statistics will be descriptive in nature, and formal sample size calculations were not performed. Phase Ib: Central randomization will be performed whereby patients will be assigned to Arm 1 (BBI608 plus sorafenib) or Arm 2 (BBI503 plus sorafenib) using block randomization. Each block will be considered a cohort with 3 subjects on Arm 1 and 3 subjects on Arm 2. After the first cohort for an Arm is complete, the dose level for the next cohort will be determined by the dose escalation rules. Safety will be summarized according to study arm. All patients receiving at least one dose of study drug (either BBI608 or BBI503) will be considered evaluable for safety analyses. Adverse events will be assessed according to CTCAE and will be evaluated by grade and organ class. Adverse event listings and tabulated summaries of categorized adverse events will be generated for all patients. Vital signs, laboratory data, and ECG data will be summarized for changes over time on study. The pharmacokinetic population will be all treated patients in a given arm with sufficient data to determine pharmacokinetic parameters. Phase II: Approximately 90 patients (30/arm) were planned to be randomized in 1:1:1 ratio into three treatment arms: Arm 1 (sorafenib plus BBI608), Arm 2 (sorafenib plus BBI503), and Arm 3 (sorafenib alone) before Amendment 3 was in effect. After amendment 3 was in effect. Arm 2 in the Phase II portion was closed for enrollment and randomization is conducted in a 1:1 ratio to the two remaining arms: Arm 1 and Arm 3. The targeted sample size remains 30 for Arm 1 and 30 Arm 3 after the amendment 3. There were approximately 10 subjects already enrolled in Arm 2 by the time amendment 3 was put into effect. Therefore, the total sample size of Phase II at the end of the trial is projected to be approximately 70 patients. Baseline characteristics as well as the observed safety, tolerability, and preliminary signs of anti-tumor activity will be summarized for each arm.

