# 2.2 Secondary Objectives

The secondary objectives for this study are:

- To determine the pharmacokinetic profile of BBI608 administered in combination with sorafenib and of BBI503 administered in combination with sorafenib.
- To perform biomarker studies for BBI608 administered in combination with sorafenib and for BBI503 administered in combination with sorafenib.

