#### 10 PLANNED STATISTICAL METHODS

# 10.1 Analysis Populations

The study populations for subsequent analyses below will be defined for phase Ib, phase II, and overall.

Enrolled Patients: A patient is considered enrolled upon receiving the first dose of

sorafenib on Cycle 1, Day 1.

Study Drug Safety Population: Defined by all patients receiving at least one dose of study drug

(either BBI608 or BBI503).

Pharmacokinetic Population: Defined as those patients who have completed all pharmacokinetic

assessments.

Dose-Escalation Population: Patients are considered evaluable for the determination of dose-

escalation if they:

a) Experience dose-limiting toxicity (DLT)

b) Complete 28-days of combination dosing at the assigned

dose-level

Population Evaluable for

Response:

The evaluable population is those patients who have received at least one cycle of study drug (either BBI608 or BBI503) and who have had at least one objective disease assessment following the

initiation of therapy.

Intent to Treat Population: All randomized patients, regardless of receiving a dose of

sorafenib or study drug.

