1.2.2. Secondary Objectives

The secondary objectives of this study are as follows:

- To determine the PK profile of napabucasin administered in combination with sorafenib and of amcasertib administered in combination with sorafenib.
- To perform biomarker studies for napabucasin administered in combination with sorafenib and for amcasertib administered in combination with sorafenib.

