3.2.2. MTD and RP2D

The maximum tolerated dose (MTD) for a given combination arm is defined as the dose level at which no more than 1 patient with a DLT is observed among 6 patients for each combination. RP2D will be determined according to safety, tolerability, and pharmacokinetics.

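### The protocol promises Cmax, Tmax, AUC and terminal half-life for both drugs, but the SAP plans only a listing of plasma concentrations

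*SAP*

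**What the plan says.** Protocol section 2.2 sets the objective: "To determine the pharmacokinetic profile of BBI608 administered in combination with sorafenib and of BBI503 administered in combination with sorafenib". SAP section 1.2.2 repeats it: "To determine the PK profile of napabucasin administered in combination with sorafenib and of amcasertib administered in combination with sorafenib". The protocol synopsis, in the item on pharmacokinetic and pharmacodynamic variables, gives the content of that profile. It opens with "Pharmacokinetic variables to be determined include maximum plasma drug" concentration (Cmax), adds Tmax, and ends with "concentration curve (AUC), and terminal half-life".

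Protocol section 6.4.1 (Tables 4 and 5) schedules serial sampling in phase Ib. Section 6.4.2 extends the complete schedule to six napabucasin patients in phase II. Other phase II patients on a study drug may have one draw, and the sorafenib-only arm has none.

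In the SAP, section 2.2 names plasma concentration of each drug as the PK endpoint. Section 7.2.3.1 gives the analysis: "Plasma concentration of napabucasin and amcasertib will be listed". The listing is to show nominal times, actual collection times and dose.

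**The concern.** The objective and the analysis do not match. The protocol commits to four derived quantities and collects timed samples to support them. The SAP replaces them with raw concentrations and stops at a listing. A programmer who follows the SAP exactly produces no parameter and no exposure summary by dose level. The study report would then have no planned output for the first of the two secondary objectives beyond individual data.

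**Working it through.** There is no sample size, power or error-rate figure to reproduce. The check is a count of scheduled samples and a comparison of what is promised with what is planned.

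**Samples per patient on the full schedule**

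- BBI608, Table 4: draws at 0, 0.5, 1, 1.5, 2, 3, 4, 6, 8, 10 and 12 h, which is 11 on Cycle 1 Day 15 and the same 11 on Cycle 2 Day 15. Total 11 + 11 = 22.
- BBI503, Table 5: draws at 0, 1, 2, 3, 4, 6, 8, 10, 12 and 24 h over Cycle 1 Days 15 and 16, which is 10; then 12, 16, 20 and 24 h after the previous night's dose on Cycle 2 Day 15, which is 4. Total 10 + 4 = 14.
- Phase II napabucasin, six patients on the full schedule: 6 × 22 = 132 draws if all are taken.

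**Promised against planned**

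| Parameter in the synopsis | Derived in the SAP | Summarised in the SAP |
|---|---|---|
| Cmax | no | no |
| Tmax | no | no |
| AUC | no | no |
| Terminal half-life | no | no |

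The count is 0 of 4, for both drugs.

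**Search for the missing step elsewhere**

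- SAP section 5 defines the intent-to-treat, safety, response evaluable and dose escalation evaluable sets. There is no PK set.
- SAP section 7.1.3 gives generic descriptive statistics for continuous endpoints. At most this would summarise concentrations.
- SAP section 7.2 summarises data by phase, arm and assigned dose level unless something else is specified, and 7.2.3.1 specifies a listing.
- SAP section 2.4 mentions population PK only as a place where covariates may be considered.
- Protocol section 10.7 says descriptive summaries of plasma levels may be generated.
- The SAP abbreviation list includes a limit of quantification, but no rule says how concentrations below it are handled.
- Neither document refers to a separate PK analysis plan or report.

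None of these yields any of the four parameters.

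**What the sampling can support**

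- BBI608, both days: Cmax, Tmax and AUC to 12 h; half-life only where the 12 h window allows it.
- BBI503, Cycle 1: Cmax, Tmax and AUC to 24 h; half-life where estimable.
- BBI503, Cycle 2 Day 15: nothing in Table 5 is drawn in the first 12 h after the dose, so the peak and full-interval AUC are not observed. A partial AUC from 12 to 24 h, or a half-life, may be estimable. Section 6.4.1.2 allows overnight sampling at selected sites, so some patients may have more.

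**Population**

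The protocol defines the PK population in two ways. The synopsis takes treated patients with enough data to derive parameters. Section 10.1 has "Defined as those patients who have completed all pharmacokinetic" assessments. The SAP adopts neither.

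**The case against.** The best defence is that the listing is a deliberate choice of scope. The SAP version history records a late clarification of how PK and pharmacodynamic data are presented in this very section, and the parameters may be derived in a PK report that we cannot see. The SAP is to be read with the protocol, section 7.1 lets further analyses be added and explained in the study report, and the listing keeps concentrations, times and doses, so the parameters can still be calculated. All of this stands as far as it goes. It means the parameters are unplanned, not lost. It does not supply a plan: a stated secondary objective should not depend on an optional addition or an uncited document.

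Three stronger readings are tempting and are not supported.

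- A reader might infer that the gap undermines the recommended phase II dose, since SAP section 3.2.2 says "RP2D will be determined according to safety, tolerability, and pharmacokinetics". The timing is against this. Protocol section 4.3 starts phase II only after that dose is determined. About 10 phase II patients were already in Arm 2 when amendment 3 took effect; the SAP's reference for that amendment is dated 2017, and SAP version 1.0 is dated 14 September 2018. The decision therefore came before the SAP. The protocol does allow the dose to be updated during phase II, but nothing shows that such an update would rest on the study report's PK output.
- A reader might infer that one missed draw out of 22 removes a BBI608 patient under protocol section 10.1. That is a literal reading. SAP section 1.1 speaks of PK assessments by sampling day, and a listing excludes nobody, so no planned output is affected. The two definitions still need reconciling before any summary is produced.
- A reader might infer that the study report cannot describe exposure by dose level. It can; the plan simply does not commit to it.

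**Conclusion.** The concern holds in limited form. The protocol names four PK parameters, schedules sampling that largely supports them, and makes the profile a secondary objective; the SAP plans none of the four for either drug. This rests on one assumption: that no separate PK plan or report covers the work. Neither document mentions one. If one exists, the defect shrinks to a missing cross-reference.

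The size is modest. The study is descriptive with no hypothesis testing, and response, survival and safety analyses are untouched. It is a cheap improvement, worth making because the samples are already scheduled and the objective is explicit.

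**What to change.** In SAP section 7.2.3.1:

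1. For patients with serial sampling, derive Cmax, Tmax, AUC to the last sample and, where estimable, half-life by non-compartmental analysis on actual times. State how concentrations below the quantification limit are handled.
2. Summarise descriptively by drug, dose level actually taken and sampling day. Actual dose matters because protocol section 7.3.2 allows holds and reductions before Cycle 2 Day 15.
3. Add a PK analysis set to SAP section 5 based on the synopsis definition (enough data to derive parameters), and reconcile protocol section 10.1 with it.
4. For BBI503 on Cycle 2 Day 15, report concentrations and, where estimable, partial AUC from 12 to 24 h or half-life. Do not report Cmax, Tmax or full-interval AUC unless overnight samples exist.
5. A comparison of Cycle 2 Day 15 with Cycle 1 Day 15 for BBI608 is optional. If made, limit it to patients on the same dose on both days, or dose-normalise it.

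If a separate PK report contains these analyses, cite it in 7.2.3.1 instead.

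The cost is modest added programming, with no new data collection. With cohorts of three to six patients the summaries will be imprecise and should be presented as descriptive only.

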7.2.3.2. Other Efficacy Endpoints Analysis

PFS and OS will be summarized and listed as appropriate. Efficacy parameters that involve disease progression as an endpoint will be derived by using both RECIST and mRECIST assessment data. The PFS and OS will be summarized with Kaplan-Meier method in the ITT analysis set with start day calculated from the date of randomization. KM analysis will not be conducted if the number of event is less than 5. Estimation and 95% confidence intervals will be provided for the proportion of patients who are alive and progression-free 4 months (PFS-4) after randomization for each arm.

Efficacy listings will be provided for best response, first CR/PR date, last date with CR or PR, most recent date without progression, progression date, death date, date of first response, date of last tumor assessment, etc.

Table 2 provides an overview of the efficacy analysis.

Table 2 Analysis Method Efficacy Endpoints

Endpoint	Analysis Set	Statistical Method	Missing Data
Response (ORR and DCR)	ITT/response evaluable analysis set	Exact CI	Observed case
Overall Survival (OS)	ITT	Kaplan-Meier	Censored at date of last contact (Appendix 1.4)
Overall Survival Follow-up Time	ITT	Reverse Kaplan-Meier	Event and censor in the original KM analysis are reversed.
Progression-Free Survival (PFS)	ITT/response evaluable analysis set	Kaplan-Meier	Censored per Table A.1.4.1 (Appendix 1.4)

7.2.4. Safety Analyses

All safety analyses will be summarized based on the safety analysis set.

7.2.4.1. Adverse Events

Overall Summary of AEs

An AE will be regarded as **treatment-emergent**, if:

- it occurs on the day of or after the first dose of napabucasin or amcasertib or a combination drug and up to 30 days after the last dose of any study drug; or
- it occurs prior to first dose date of napabucasin or amcasertib or a combination drug and worsens in severity on therapy and up to 30 days after the last dose of study drug.

Adverse events will be coded by SOC and PT using the MedDRA v19.0. The severity of AEs will be graded by the investigator using (NIH NCI CTCAE Version 4.0). The verbatim term will be included in the AE listings.

An overview of treatment-emergent adverse events (TEAEs) will be provided. The number and percentage of patients will be summarized for:

- Patients with at least one TEAE
- Patients with TEAEs of CTCAE Grade 3 or higher
- Patients with serious TEAEs
- Patients with napabucasin-related TEAEs

- Patients with napabucasin-related TEAEs of CTCAE Grade 3 or higher
- Patients with amcasertib-related TEAEs
- Patients with amcasertib-related TEAEs of CTCAE Grade 3 or higher
- Patients with sorafenib-related TEAEs
- Patients with sorafenib-related TEAEs of CTCAE Grade 3 or higher
- Patients with napabucasin-related serious TEAEs
- Patients with napabucasin-related serious TEAEs of CTCAE Grade 3 or higher
- Patients with amcasertib-related serious TEAEs
- Patients with amcasertib-related serious TEAEs of CTCAE Grade 3 or higher
- Patients with sorafenib-related serious TEAEs
- Patients with sorafenib-related serious TEAEs of CTCAE Grade 3 or higher
- Patients with TEAEs leading to napabucasin dose hold
- Patients with TEAEs leading to dose reduction of napabucasin
- Patients with TEAEs leading to amcasertib dose hold
- Patients with TEAEs leading to dose reduction of amcasertib
- Patients with TEAEs leading to sorafenib dose hold
- Patients with TEAEs leading to dose reduction of sorafenib

Summary of AEs during Run-in Period

Besides overall summary of AEs as described above, the analysis of AEs during Run-in period will be summarized separately. Run-in Period is defined from the first sorafenib dose date to one day prior to patient administrated the napabucasin/amcasertib, or to the end of treatment if patient discontinued the study treatment before the napabucasin/amcasertib administration. For Phase II sorafenib monotherapy arm patients, run-in period is defined as the first 14 days of sorafenib administration.

An overview of TEAEs during Run-in period will be provided. The number and percentage of patients will be summarized for:

- Patients with at least one TEAE
- Patients with TEAEs of CTCAE Grade 3 or higher
- Patients with serious TEAEs
- Patients with serious TEAEs of CTCAE Grade 3 or higher
- Patients with sorafenib-related TEAEs
- Patients with sorafenib-related TEAEs of CTCAE Grade 3 or higher
- Patients with sorafenib-related serious TEAEs
- Patients with sorafenib-related serious TEAEs of CTCAE Grade 3 or higher
- Patients with TEAEs leading to sorafenib dose hold
- Patients with TEAEs leading to dose reduction of sorafenib

Summary of Overall AEs and AEs during Run-in Period by System Organ Class and Preferred Term

The number and percentage of patients with overall AEs and AEs during run-in period by SOC and PT and maximum CTCAE grade will be summarized. A summary of TEAEs of CTCAE grade 3 or higher (Grade 3, 4, 5) will be presented by SOC and PT and maximum CTCAE grade.

Treatment-Related TEAEs

TEAEs reported with a relationship to a treatment considered by the investigator to be ‘possible’, ‘probable’ or ‘definite’ will be considered “Related” to either the study treatment or a combination drug. Missing relationships will be considered as “Related”.

Serious AEs and Death

Treatment-emergent SAEs and treatment-related SAEs will be summarized by MedDRA SOC and PT and maximum CTCAE grade.

Patients who experience an SAE during the AE reporting period will be listed for all safety patients. The number and percentage of patients who experience any treatment-emergent SAE will be summarized by SOC, PT, and maximum CTCAE grade. A similar summary for treatment-related treatment-emergent SAEs will be provided also.

Deaths that occur on the same day or after the first dose of study treatment and within 30 days of the last dose of any study treatment will be summarized. The number and percentage of patients who died during the study treatment and within 30 days after the last dose will be presented.

A listing of death data will also be provided and will include all deaths that occurred during the reporting period for deaths, which starts from the signing of the informed consent to the end of the follow-up period. The listing will include date of death and the number of days relative to the administration of the first and last dose.

Adverse Events of Clinical Relevance

Selected AEs were pre-specified for additional focus due to the potential clinical significance of the event and/or the potential association with the investigational product. These events include those in the standardized MedDRA query (SMQ) (narrow or broad, as noted):

Table 3 Adverse Events of Clinical Relevance SMQ Terms

MedDRA v19.0 Term	SMQ class
Ventricular fibrillation	NA (individual PT)
Ventricular tachycardia	NA (individual PT)
Non-infectious diarrhea	Broad
Gastrointestinal haemorrhage	Narrow

Gastrointestinal obstruction	Narrow
Acute kidney injury	Narrow (acute renal failure)

Tables listing the incidence, maximum severity, and drug relationship of these events in the safety population will be generated.

Adverse Events Leading to a Study Drug Discontinuation

Adverse Events leading to a study drug discontinuation will be identified based on any AEs collected on CRF End of Treatment page along with study drug hold action on Adverse Events page.

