#### 5 STUDY VISITS

#### 5.1 Overview

For the phase Ib portion of the study, study visits will consist of a Pre-Study Evaluation, during which the patient will be evaluated to determine eligibility for entry into the study; a Cycle 1, Day 1 Visit at the start of the sorafenib monotherapy run-in period; a phone call to patients on Cycle 1, Day 8, which is the approximate mid-point of the 14-day sorafenib monotherapy run-in period; a Cycle 1, Day 15 Visit, which is the start of combination therapy; a Cycle 1, Day 22 visit; and then regular evaluations every 2-weeks starting on Cycle 2, Day 1.

For the phase II portion of the study, study visits will also involve a Pre-Study Evaluation. Cycle 1 visits will include a brief visit on Cycle 1, Day 1 (the start of the sorafenib monotherapy run-in period); a phone call to patients on Cycle 1, Day 8; a full visit on Cycle 1, Day 15 (the start of combination therapy); and a visit on Cycle 1, Day 22. In Cycle 2, there will be visits on Cycle 2, Day 1 and on Cycle 2, Day 15. Starting in Cycle 3, the only required in-person visit is on the first day of the study cycle (i.e., Cycle 3, Day 1; Cycle 4, Day 1, etc.).

During the phase II portion, an in-person visit on Cycle 3, Day 15 is optional, and is optional on Day 15 of each subsequent cycle, provided patients are stable. If the in person visit is not performed on Cycle 3, Day 15 or on Day 15 of a subsequent cycle, study staff are to reach out to the patient with a phone call.

For both phase Ib and phase II, an End-of-Study Evaluation will also be completed between 14 and 30 days after the last dose of protocol therapy; See Section 14 for a schedule of Assessments).

In general, unless otherwise noted, a window of  $\pm$  2 days is allowed when scheduling protocol visits and evaluations. If, due to unforeseen circumstances, frame-shifting of a study cycle or patient visit schedule occurs beyond the allowable window of  $\pm$  2 days, the medical monitor for the Sponsor should be notified of the alternate schedule. The protocol window of  $\pm$  2 days may then be applied to the frame-shifted schedule.

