1.1. Study Design

Phase Ib

This is an open label, phase 1b dose escalation study of napabucasin (BBI608) administered in combination with sorafenib (Arm 1), and amcasertib (BBI503) administered in combination with sorafenib (Arm 2) to patients with advanced hepatocellular carcinoma (HCC). Eligible patients will be randomized to either Arm 1 or Arm 2. The study is designed to explore the safety, tolerability and pharmacokinetics (PK) of napabucasin and amcasertib, and to define a recommended Phase II dose (RP2D) of napabucasin and amcasertib when administered in combination with sorafenib.

In Arm 1, initially 3 patients will be enrolled at napabucasin Dose-Level 1. Dose escalation will proceed with cohorts of 3 to 6 patients according to the criteria for dose escalation and the criteria for determining dose-limiting toxicity (DLT).

Napabucasin Dose Level	Napabucasin Dose & Schedule
Napabucasin Dose-Level I	160 mg Twice Daily
Napabucasin Dose-Level II	240 mg Twice Daily

In Arm 2, initially 3 patients will be enrolled at amcasertib Dose-Level 1. Dose escalation will proceed with cohorts of 3 to 6 patients according to the criteria for dose escalation and the criteria for determining DLT.

Amcasertib Dose Level	Amcasertib Dose & Schedule
Amcasertib Dose-Level I	100 mg Once Daily
Amcasertib Dose-Level II	200 mg Once Daily

Prior to initiation of combination therapy in each arm, sorafenib will be administered as monotherapy starting on Cycle 1, Day 1 for 14 days. Sorafenib will be administered at a fixed dose of 400 mg twice daily (800 mg total daily dose) for each arm and for each dose-level cohort. Dose-adjustment of sorafenib according to the approved product label is allowed. Following the sorafenib run-in period, the combination regimen will begin on Cycle 1, Day 15. Protocol therapy will continue in repeating 28-day cycles until disease progression, unacceptable toxicity, or another discontinuation criterion is met.

For both arms, PK assessments will be performed on Cycle 1, Day 15 and Cycle 2, Day 15. An additional PK assessment may be performed to confirm exposure following dose modification. Once the RP2D is determined for both study arms, the phase II portion will begin.

Phase II

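### The run-in adverse event window is uncapped in Arms 1 and 2 but fixed at 14 days in Arm 3, so the Phase II run-in percentages are not on a common window when study drug starts off schedule or is never started

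*SAP*

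**What the plan says.** SAP 7.2.4.1 (Summary of AEs during Run-in Period) gives two rules for one table.

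- Arms 1 and 2: "Run-in Period is defined from the first sorafenib dose date to one day prior to patient administrated the napabucasin/amcasertib". A patient who never receives either drug has a window that closes when treatment ends. No maximum length is stated.
- Arm 3, which exists only in Phase II: the "run-in period is defined as the first 14 days of sorafenib administration".

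The planned schedule is the same length in every arm. SAP 1.1 says that "sorafenib will be administered as monotherapy starting on Cycle 1, Day 1 for 14 days" and that "Following the sorafenib run-in period, the combination regimen will begin on Cycle 1, Day 15". Protocol 5.1 gives the same Day 15 start for Phase II. The same section says that a window of ±2 days "is allowed when scheduling protocol visits and evaluations", and it accepts larger shifts if the medical monitor is notified, with no upper limit.

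The run-in table reports counts and percentages of patients, with no adjustment for time at risk. The safety set (SAP 5.2) includes anyone who took sorafenib, so patients in Arms 1 and 2 who never reach study drug are in the table.

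**The concern.** During the run-in all arms receive the same single drug. A reader of the Phase II table will therefore take a difference between arms as chance or as a difference between the patients. That reading needs the same observation time in each arm. Here the time depends on when study drug starts, or whether it starts, in Arms 1 and 2 but not in Arm 3. A patient whose start slips is observed longer than a comparable Arm 3 patient. A patient who stops in the first days may be observed for less.

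Safety and tolerability are part of the Phase II primary objective, and Protocol 4.1 describes Phase II as designed to compare them. The absence of hypothesis tests (SAP 3.1) does not remove the issue, because the descriptive percentages are what readers will set side by side.

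**Working it through.** **1. Window length, from the two definitions.** In Arms 1 and 2 the length is the study-drug start day minus 1; in Arm 3 it is 14. Days 13 and 17 are the edges of the ±2-day visit window. Days 22 and 29 are assumed delays.

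| Study-drug start | Arms 1/2 window (days) | Arm 3 window (days) | Ratio |
|---|---|---|---|
| Day 13 | 12 | 14 | 0.86 |
| Day 15 (planned) | 14 | 14 | 1.00 |
| Day 17 | 16 | 14 | 1.14 |
| Day 22 | 21 | 14 | 1.50 |
| Day 29 | 28 | 14 | 2.00 |

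The Day 15 row reproduces the SAP's 14 days, so on schedule there is no difference.

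**2. Risk for one patient.** The documents give no run-in AE rate. Let p be an assumed 14-day risk with constant hazard; the risk over L days is R(L) = 1 − (1 − p)^(L/14).

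| p | 12 days | 16 days | 21 days | 28 days |
|---|---|---|---|---|
| 10% | 8.6% | 11.3% | 14.6% | 19.0% |
| 30% | 26.3% | 33.5% | 41.4% | 51.0% |
| 50% | 44.8% | 54.7% | 64.6% | 75.0% |

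**3. Effect on Arm 1.** The target is 30 patients each in Arms 1 and 3 (Protocol 10.3). Suppose a fraction f of Arm 1 starts late (assumed 10–30%), independently of earlier events, and the rest start on Day 15. The excess over Arm 3 is f × (R(L) − p).

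- Smallest case: f = 10%, p = 10%, L = 16. 0.10 × (11.3 − 10.0) = 0.1 points, or 0.04 of 30 patients.
- Middle case: f = 20%, p = 30%, L = 21. 0.20 × (41.4 − 30.0) = 2.3 points, or 0.7 of 30 patients.
- Largest case: f = 30%, p = 50%, L = 28. 0.30 × (75.0 − 50.0) = 7.5 points, or 2.25 of 30 patients.

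Across the grid the excess is 0.1–1.4 points for 16-day windows, 0.5–4.4 for 21-day and 0.9–7.5 for 28-day. These are ends of an assumed range, not limits: the SAP sets no cap.

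**4. The opposite direction.** An Arm 1 patient who stops treatment on Day 7 has a 7-day window. If Arm 3's 14 days are calendar days, the same patient there has 14. At p = 30% the risks are 1 − 0.70^(7/14) = 16.3% and 30%. The SAP does not say whether the 14 days are calendar or dosing days, or whether they end at early discontinuation.

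**5. What is not touched.** The overall treatment-emergent summary in SAP 7.2.4.1 counts events from the first dose of any of the drugs to 30 days after the last dose. Events during a delay stay in it for every arm.

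**The case against.** The best defence is that the rule follows treatment. In Arms 1 and 2 it captures all sorafenib-only time and separates it from study-drug exposure. Arm 3 has no study-drug date, so the planned 14 days is a natural stand-in. The schedule puts the start on Day 15, Protocol 5.1 reserves larger shifts for unforeseen circumstances, and the table is descriptive and supplementary. All of this stands, and it keeps the point small. It does not make the windows equal for patients off schedule.

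Four stronger readings are tempting, and the documents do not support them.

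- A reader might infer that run-in rates must differ between arms. They need not: the windows are identical for every Day 15 start.
- A reader might infer that the table will overstate sorafenib toxicity in Arms 1 and 2. Early starts, and stops before Day 14, work the other way.
- A reader might infer that the excess grows when toxicity itself causes the delay. For the same table row it does not. Each patient counts once, so a patient delayed by a Grade 3 event in Days 1–14 is already in the Grade 3 or higher row, and a longer window adds nothing. If only such patients were delayed, that row would show no excess. Some inflation remains possible when a milder event causes the delay and a worse or different one follows. The documents do not say how often toxicity delays the start.
- A reader might infer that events in the delay period are lost from a post-run-in comparison. The SAP plans no such table.

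**Conclusion.** The two definitions are inconsistent, and the Phase II run-in percentages are not guaranteed to rest on a common window. The effect is confined to patients whose study drug starts off Day 15 or never starts, and the net direction cannot be stated in advance. The late-start excess calculated above, at most about 2 patients of 30, rests wholly on assumed delay frequencies, delay lengths and event risks, on a constant hazard, and on delay being independent of earlier events. With every start on Day 15 it is zero. This is a small but avoidable flaw in one descriptive Phase II table; the main safety summary stands as planned.

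**What to change.** In SAP 7.2.4.1, use one rule for all Phase II arms: from the first sorafenib dose to the earlier of calendar Day 14 and the day before the first napabucasin or amcasertib dose. State that days are calendar days. Handle early discontinuation identically in every arm, for instance by ending the window at end of treatment in all three. Show events in Arms 1 and 2 from Day 15 to a delayed first study-drug dose in a separate row, so that no sorafenib-only event is lost.

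No window then exceeds 14 days, so the late-start excess and the early-stop mismatch both go. A Day 13 start still gives 12 days, because sorafenib-only time really ends there.

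The cost is a short edit to the SAP text, one changed date derivation and one extra table row. Treatment and data collection do not change. The only downside is that a few delayed-start events move from the main run-in rows to the separate one.
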